**Table 12-1 BLESS III Study Visit Schedule: List of Activities and Parameters to be assessed at Each Study Visit**

VISIT 	TIME 	ACTION
Visit 1  Screening	0 to 14 days	Informed consent ( Section 12.1 ) Inclusion and exclusion criteria ( Section 10 ) Medical history ( Section 14.11 ) Demographic data ( Section 14.14 ) Urine dip stick pregnancy test (all applicable subjects, Section 14.12 ) Physical examination ( Section 14.11 ) Vital signs ( Section 14.13 ) Concomitant medication ( Section 14.10 ) GLS-I ( Sections 13.1.1 and 23.1 ) GLS-S ( Section 13.1.1 and 23.2 )
Visit 2  Treatment	Baseline Day 0	Urine dip stick pregnancy test (all applicable subjects, Section 14.12 ) Vital signs ( Section 14.13 ) Concomitant medication ( Section 14.10 ) GLS-I ( Sections 13.1.1 and 23.1 ) GLS-S ( Section 13.1.1 and 23.2 ) Photography ( Section 13.1.2 ) Inclusion and exclusion criteria  ( Section 10 ) AE assessment ( Section 14 ) AESI questioning pre-dose  ( Section 14.2 ) TREATMENT ( Section 11.3 ) Post-treatment observation as well as AE and AESI assessment after 30 minutes  Distribute Subject Diary ( Section 12.5 )
Visit 3 Week 1	7 days ± 2 days after Baseline	Collect/Review/Distribute Subject Diary ( Section 12.5 ) Vital signs ( Section 14.13 ) Concomitant medication ( Section 14.10 ) GLS-I ( Sections 13.1.1 and 23.1 ) GLS-S ( Section 13.1.1 and 23.2 ) AE and AESI assessment ( Section 14 )
Visit 4 Week 2	14 days ± 5 days after Baseline (Day 0)	Collect Subject Diary ( Section 12.5 ) Concomitant medication ( Section 14.10 ) GLS-I ( Sections 13.1.1 and 23.1 ) GLS-S ( Section 13.1.1 and 23.2 ) Photography ( Section 13.1.2 ) AE and AESI assessment ( Section 14 )

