Visit 5 Week 4	4 weeks ± 2 days after Baseline (Day 0)	Urine dip stick pregnancy test ( applicable subjects in Austria only , Section 14.12 ) Vital signs ( Section 14.13 ) Concomitant medication ( Section 14.10 ) GLS-I ( Sections 13.1.1 and 23.1 ) GLS-S ( Section 13.1.1 and 23.2 ) Photography ( Section 13.1.2 ) FACE-Q Satisfaction with Outcome Scale ( Sections 13.2 and 23.3 ) AE and AESI assessment ( Section 14 )
Visit 6 Week 8	8 weeks ± 5 days after Baseline (Day 0)	Urine dip stick pregnancy test (applicable subjects in Austria only, Section 14.12 ) GLS-I ( Sections 13.1.1 and 23.1 ) GLS-S ( Section 13.1.1 and 23.2 ) Concomitant medication ( Section 14.10 ) AE and AESI assessment ( Section 14 )
Visit 7 Week 12	12 weeks ± 5 days after Baseline (Day 0)	Urine dip stick pregnancy test (applicable subjects in Austria only, Section 14.12 ) Vital signs ( Section 14.13 ) Concomitant medication ( Section 14.10 ) GLS-I ( Sections 13.1.1 and 23.1 ) GLS-S ( Section 13.1.1 and 23.2 ) Photography ( Section 13.1.2 ) FACE-Q Satisfaction with Outcome Scale ( Sections 13.2 and Section 23.3 ) AE and AESI assessment ( Section 14 )
Visit 8  Week 16 End of Study	16 weeks ± 5 days after Baseline (Day 0)	Urine dip stick pregnancy test (all applicable subjects, Section 14.12 ) Physical examination ( Section 14.11 ) Vital signs ( Section 14.13 ) Concomitant medication ( Section 14.10 ) GLS-I ( Sections 13.1.1 and 23.1 ) GLS-S ( Section 13.1.1 and 23.2 ) Photography ( Section 13.1.2 ) FACE-Q Satisfaction with Outcome Scale ( Sections 13.2 and 23.3 ) AE and AESI assessment ( Section 14 )

 An unscheduled visit is permitted, if necessary. Assessments performed at an unscheduled visit will be at the investigator's discretion, but should include AE assessment, AESI query, concomitant medication and possibly GLS-I/GLS-S.

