## 12.5 Subject Diary and Patient Reported Outcomes

### 12.5.1 Subject Diary

A paper subject diary will be provided to each subject at Visit 2, Baseline (Day 0) and at Visit 3 (Week 1) for daily documentation of GLS-S score at maximum frown. Subjects will be trained on use of the diary during the Baseline visit and the training will be recorded in the source.

The first subject diary will be collected at Visit 3 (Week 1) one week after treatment; the second diary will be collected at Visit 4 (Week 2), two weeks after treatment. The diary shall be checked for completeness at both visits to ensure all required data has been entered.

The subject will record the GLS-S score in diaries daily for the first two weeks after treatment.

The subject diary will serve as a source record. Entries in the subject diary will be transcribed into the electronic data capture (EDC) system by the blinded member of the site study team.

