## 7 STATISTICAL CONSIDERATIONS AND ANALYSIS

### 7.1 Derived Variables

The below table provide the list of derived variables for various duration derivations and Baseline derivations applicable for this study.

Variables	Formula
Derivation of Duration	
Study day at any visit	Date of interest – date of first dose of study drug, if date of interest is before date of first dose of study drug. Date of interest – date of first dose of study drug + 1, otherwise.
Baseline Derivations	
Baseline	The Baseline value is defined as the last observation before treatment, i.e., pre-treatment values measured on the treatment day (Baseline visit, Day 0), and if missing or not evaluated, the value from the screening visit will be used. Baseline will be missing if no values have been measured before treatment.
Change from Baseline	Post-Baseline value – Baseline value
Relative change from Baseline	[(Post-Baseline value – Baseline value)/Baseline value]*100

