### **8.6.3 Analysis of Secondary Efficacy Endpoints**

Since the focus of the statistical analysis is on descriptive statistics and no formal statistical hypothesis testing is planned on secondary endpoints, no adjustment for controlling the type 1 error rate is required.

For the below categorical endpoints,

- Percentage of responders with an FWS score of 0 or 1 and a  $\geq 1$  point reduction in FWS score at maximum frown at Weeks 1, 2, 8, 12 and 16, based separately on independent investigator assessments and subject assessments
- Percentage of responders with an FWS score of 0 or 1 and a  $\geq 2$  point reduction in FWS score at maximum frown at Weeks 1, 2, 4, 8, 12 and 16, based separately on independent investigator assessments and subject assessments
- Percentage of responders with an FWS score of 0 or 1 and a  $\geq 1$  point reduction in FWS score at rest at Weeks 1, 2, 4, 8, 12 and 16, based separately on independent investigator

assessments and subject assessments

the same analyses will be conducted as described for the co-primary endpoints.

For investigator assessments, subjects with missing FWS investigator assessment at Baseline or at the post-Baseline visit will be assigned as non-responders.

For subject assessments, subjects with missing FWS subject assessment at Baseline or at the post-Baseline visit will be assigned as non-responders.

The analyses of these secondary endpoints will also be conducted on observed values.

For investigator assessments, subjects with missing FWS investigator assessment at Baseline or at the post-Baseline visit will be excluded from the analysis but not assigned as being non-responders.

For subject assessments, subjects with missing FWS subject assessment at Baseline or at the post-Baseline visit will be excluded from the analysis but not assigned as being non-responders.

Appropriate descriptive statistics will be provided for the secondary endpoint analyses.

The following secondary endpoints will be analyzed descriptively using Kaplan-Meier time to event methodology

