- Time to onset of effect, as measured at Weeks 1, 2, and 4, based separately on independent investigator assessments and subject assessments. Onset of effect is defined as  $\geq 1$  point improvement in Glabellar Line Scale - Investigator (GLS-I) and Glabellar Line Scale – Subject (GLS-S) score relative to Baseline at maximum frown in glabellar lines. In addition, onset of effect will be assessed by subjects daily during the first 2 weeks after treatment, by recordings in the subject diary.
- For subjects who respond, duration of effect will be assessed separately based on independent investigator assessments and subject assessments. Effect will be deemed to be lost when scores return to individual Baseline values.

Duration of effect is defined as the date that loss of response occurred – date of IMP Injection

+1. Whereas the loss of response is considered when the response returns to the individual “baseline” grade or worse for Week 4 responder (defined as by having achieved FWS score of 0 or 1 and a  $\geq 1$  point reduction in FWS score at maximum frown at the Week 4 Visit) on FWS at maximum frown. For example, if a subject has a Baseline FWS of 3, the loss of response will be considered when the post-Baseline FWS returns to 3. Duration of effect will be derived separately based on investigator assessments and subject assessments.

For responders that maintain response, censoring will be done at the last visit where FWS grade at maximum frown is assessed.

Survival statistics such as the Kaplan-Meier estimator of the median will be presented.

The FACE-Q assessment at Weeks 4, 12 and 16 will be analyzed descriptively (n and % will be presented).

The FACE-Q Satisfaction with Outcome Scale will be derived in accordance with the developers' instructions and missing data treated accordingly.

The FAS population will serve as the primary analysis set for the descriptive statistics.

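### In-clinic time to onset is first assessed at Week 1, so if at least half of an arm has improved by then, its Kaplan-Meier median is a Week 1 visit date

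*SAP*

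**What the plan says.** SAP 8.6.3 lists this secondary endpoint: "Time to onset of effect, as measured at Weeks 1, 2, and 4, based separately on independent investigator assessments and subject assessments". Onset is an improvement of at least 1 point in GLS-I or GLS-S "score relative to Baseline at maximum frown in glabellar lines". The endpoint is to be "analyzed descriptively using Kaplan-Meier time to event methodology", and the section names the Kaplan-Meier median as a statistic to present. It gives no interval-censored method and no rule for dating onset. The Kaplan-Meier choice comes from Protocol 15.4.2, which counts time to onset among the key secondary endpoints.

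Protocol Table 12-1 puts the Week 1 visit at "7 days ± 2 days after Baseline". Week 2 is 14 days with a 5-day margin and Week 4 is 28 days with a 2-day margin. No GLS-I is scheduled between treatment and Week 1. Unscheduled results go to listings only unless otherwise stated (SAP 8.1), and 8.6.3 states nothing different for onset.

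The same item in SAP 8.6.3 also includes a daily diary. Protocol 12.5.1 says: "The subject will record the GLS-S score in diaries daily for the first two weeks after treatment". The diary covers maximum frown and is completed by the subject, with no investigator counterpart.

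**The concern.** The study title names time to onset as one of three comparisons, and secondary objective 4 asks for it by investigator as well as subject assessment. The daily diary suggests that onset was expected on a scale of days. For anyone already improved at Week 1, however, the clinic record shows only that onset came before that visit. A different censoring method cannot recover a time that nobody observed.

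No hypothesis test is planned, so the printed estimate is the result. In-clinic medians of about 7 days in both arms could be taken as equal onset when they mainly reflect when visits were booked. The statistic can also err the other way. If one arm has fewer than half of its subjects improved by Week 1, its median moves to the Week 2 visits and the gap can be exaggerated.

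**Working it through.** **Inputs from the documents.** 100 subjects per group (Protocol 15.1). Visit windows of Day 5 to 9, Day 9 to 19 and Day 26 to 30, counting treatment as Day 0 (Protocol Table 12-1). SAP 7.1 defines post-dose study day as "Date of interest – date of first dose of study drug + 1, otherwise", so Day 5 to 9 is study day 6 to 10 on that scale.

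**The plan's own figure.** The only design figure is the half-width of the 95% CI for the Week 4 responder difference: 1.96 × √(2 × 0.815 × 0.185 / 100) = 0.1076, the stated 10.8%. It is reproduced. Nothing comparable is given for onset.

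**What the median must be.** Let q be the share of an arm with onset by its Week 1 visit.
- On nominal days, the survival estimate falls from 1 to 1 − q at Day 7, so the median is Day 7 whenever q is at least 0.5.
- On actual dates, and if onset status is unrelated to the visit day chosen, the median is the 0.5/q quantile of the Week 1 visit dates. For q = 0.60, 0.80 and 0.99 that is the 83rd, 62nd and 51st percentile.

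This follows from the estimator and needs no onset distribution.

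**Size, under assumptions.** Onset is taken as lognormal with log-SD 0.5, so the share with onset by day t is F(t) = Φ(ln(t/median)/0.5).

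*All Week 1 visits on Day 7*

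| True median (days) | ln(7/median)/0.5 | Onset by Week 1 | Kaplan-Meier median |
|---|---|---|---|
| 2 | 2.51 | 99% | 7 |
| 4 | 1.12 | 87% | 7 |
| 3 | 1.69 | 96% | 7 |
| 5 | 0.67 | 75% | 7 |

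The difference in medians is 0 for both 2 v 4 and 3 v 5 days. It was 0 in every one of 3,000 simulated trials of 100 per arm.

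*Week 1 visits spread evenly over Day 5 to 9.* The share recorded with onset by Day d is one fifth of F(5) + … + F(d).

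| True median (days) | By Day 7 | By Day 8 | By Day 9 (all Week 1 visits) | Median falls on |
|---|---|---|---|---|
| 2 | 59% | 79% | 99% | Day 7 |
| 4 | 47% | 65% | 84% | Day 8 |
| 3 | 54% | 74% | 94% | Day 7 |
| 5 | 38% | 54% | 72% | Day 8 |

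Over 3,000 simulated trials the mean difference in medians was 0.7 day for 2 v 4 and 1.0 day for 3 v 5, against a true 2 days. Daily recording, as in the diary, gave about 2.0 days in both cases.

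**A different onset shape.** A Weibull model (shape 2, 400 runs) with most visits on Day 7 gave 7.0 v 7.0 for true 2 v 4 days and 7.0 v 7.1 for 3 v 5. For true 4 v 8 days, with 88% v 41% improved by Day 7, it gave 7.0 v 13.1. That is a gap of 6.1 days against a true 4.

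**What by-visit proportions show.** With Day 7 visits and 99/100 v 87/100, the Wilson limits are 94.5% to 99.8% and 79.0% to 92.2%. The Newcombe lower limit is 0.12 − √((0.990 − 0.9455)² + (0.9224 − 0.870)²) = 0.051. The upper limit is 0.12 + √((0.9982 − 0.990)² + (0.870 − 0.7902)²) = 0.200. The difference of 12 points (95% CI 5 to 20) is visible where the difference in medians is 0.

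**The case against.** A reader might infer that the trial cannot measure the onset difference named in its title. The documents do not support that. The title does not say investigator-rated, and the diary is part of the same endpoint and times subject-rated onset to the day.

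A reader might also infer that the two in-clinic medians will always coincide. They need not. If actual dates are used they can differ by about a day, although that gap depends on visit booking and on the Week 1 proportion and does not measure the onset difference.

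Several points on the other side stand:
- The endpoint already says that it is measured at Weeks 1, 2 and 4, so day-level investigator timing was never promised.
- The median is given only as an example of the statistics to present. With nominal visits and no earlier censoring, one minus the Kaplan-Meier estimate at Week 1 is the proportion with onset by Week 1. The analysis therefore keeps the information. The gap is that this proportion, and an interval for its difference, are not named as outputs.
- Kaplan-Meier is specified in the protocol, which argues for adding a summary and against deleting one.
- The size depends on assumed onset times. The zero difference and the 0.7 to 1.0 day difference come from different assumptions about visit dates.

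One point stands only in part. Responder rates by investigator and by subject at Weeks 1 and 2, with Newcombe intervals, are already planned. For a Baseline score of 2 the responder definition and onset coincide. A subject who goes from 3 to 2 has onset but is not a responder, so that table does not replace onset by visit.

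**Conclusion.** The concern holds for in-clinic onset, by GLS-I and by in-clinic GLS-S. If at least half of an arm has improved by Week 1, that arm's Kaplan-Meier median is a Week 1 visit date. Whether that happens is unknown, because the documents give no onset time or Week 1 onset rate.

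Under the lognormal assumption, a true 2-day difference shrinks to between 0 and about 1 day in the medians, depending on how visits fall in their windows. The Week 1 proportions still separate the arms by roughly 12 to 15 points (2 v 4 days) or 21 to 22 points (3 v 5 days). If onset is slower and one arm is below half at Week 1, the distortion changes form and can exaggerate the gap.

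The limit does not reach diary-based onset. The endpoint is secondary, descriptive and untested, so the primary results and the sample size are unaffected. The change is still worth making, because the in-clinic comparison can be made informative with data and methods already planned.

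**What to change.** In SAP 8.6.3:
1. Name the daily diary GLS-S as the main source for time to onset in days.
2. For GLS-I and in-clinic GLS-S, add the proportion with onset by Week 1, by Week 2 and by Week 4, with the between-arm difference and Newcombe 95% CI. Make this the main in-clinic onset summary.
3. Apply the missing-data rule that 8.6.3 already gives for the categorical secondary endpoints: missing counted as no onset, repeated on observed values. Cite that rule explicitly, because SAP 7.2.1 refers to observed data only for endpoints other than the co-primaries.
4. Keep the protocol-specified Kaplan-Meier curve, and state that its in-clinic median is not to be interpreted as onset in days.
5. Record the addition in SAP section 9.

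The cost is one extra table and a few lines of text, using scores already collected and an interval method already specified. The downside is less weight on an in-clinic median in days.

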## 12.7 Procedures for Monitoring Subject Compliance

All study procedures are to be performed under supervision at the study site, and thus, no separate procedures will be used to monitor subject compliance.

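### The Week 2 window lets the onset diary be collected from Day 9 although 14 days of entries are required, and the SAP does not say how the diary dates onset

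*SAP*

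**What the plan says.** **What is collected.** Protocol 12.5.1 provides paper diaries at Baseline and at Week 1 for self-rated severity at maximum frown: "The subject will record the GLS-S score in diaries daily for the first two weeks after treatment". On return it says "the second diary will be collected at Visit 4 (Week 2), two weeks after treatment". The Visit 4 row of Table 12-1 gives the timing as "14 days ± 5 days after Baseline (Day 0". Protocol 9.3.4 confirms a 5-day tolerance for every visit except Weeks 1 and 4, where it is 2 days.

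**How onset is analysed.** SAP 8.6.3 defines onset as an improvement of at least 1 point from Baseline at maximum frown, measured in clinic at Weeks 1, 2 and 4. It adds that "onset of effect will be assessed by subjects daily during the first 2 weeks after treatment, by recordings in the subject diary". The method is stated in one line: "The following secondary endpoints will be analyzed descriptively using Kaplan-Meier time to event methodology". The section does not say whether the diary date is the first or a sustained improvement, or whether diary and clinic self-ratings are combined. It gives no censoring rule for onset. Duration of effect, in the same section, has a formula, a worked example and a censoring rule: "For responders that maintain response, censoring will be done at the last visit where FWS grade at maximum frown is assessed".

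**Supervision.** Protocol 12.7 states "All study procedures are to be performed under supervision at the study site" and on that ground plans no separate compliance monitoring. SAP 8.5.2 repeats this.

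**The concern.** Time to onset is in the study title and is listed as a key secondary endpoint in Protocol 15.4.2. The first clinic look falls between Day 5 and Day 9, so only the diary can date onset before then.

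Two things weaken it. The collection window does not fit the required recording period, so a site that follows the protocol exactly can return an incomplete diary. And an event defined only by a threshold, on a 4-point scale rated every day, will by default be programmed as the first day the threshold is met. Each day before true onset is then a chance for a stray low rating to be taken as onset. The slower arm has more such days, so equal error rates in the two arms would narrow a real difference between them. With no rule in the SAP, the choice is left to programming.

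**Working it through.** **The plan's own figure.** The only statistical figure stated is the half-width of the 95% confidence interval for the difference in Week 4 responder rates: 1.96 × √(2 × 0.815 × 0.185 / 100) = 0.1076, which matches the stated 10.8%. It has no bearing on onset. The documents give no onset distribution and no rating-error rate, so steps 2 to 4 rest on assumptions shown as ranges.

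**1. Diary days at risk (documents only).**
- Week 2 window: 14 − 5 = Day 9 to 14 + 5 = Day 19, with the treatment day as Day 0. SAP 7.1 counts the treatment day as 1, so Day 9 is SAP study day 10.
- Required entries: 14 days. Collection on Day 9 loses 14 − 9 = 5 of 14.
- If visits were spread evenly over the 11 possible days (an assumption), 5/11 = 45% would precede Day 14 and the mean loss would be (5 + 4 + 3 + 2 + 1)/11 = 1.36 days.

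**2. Onsets falling in the lost days.** With onset lognormal (median m, log-SD 0.5), the share between Day 9 and Day 14 is Φ(ln(14/m)/0.5) − Φ(ln(9/m)/0.5).

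| Assumed median | All collected on Day 9 | Averaged over Days 9-19 | Day 9, Weibull shape 2 or 1 |
|---|---|---|---|
| 3 days | 1.3% | 0.2% | 0.2% or 8.6% |
| 4 days | 4.6% | 0.9% | 3.0% or 12.2% |
| 6 days | 16.4% | 3.6% | 18.7% or 15.5% |

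**3. False early onset under a first-day rule.** With stray-rating probability f per day, independent between days, and k days before true onset, P = 1 − (1 − f)^k. For k = 6 and f = 1%, 2%, 5%, 10% this gives 5.9%, 11.4%, 26.5%, 46.9%. The chance of two consecutive stray days within the same six is 0.05%, 0.2%, 1.2%, 4.6%.

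**4. Effect on the comparison.** Simulated onset is lognormal with medians 3 and 4 days and log-SD 0.5. Stray ratings occur in either direction over 14 diary days. The true mean difference is 1.13-1.14 days, and loss = 1 − observed/true.

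| Stray ratings per day | First-day rule (days) | Loss | Two-day rule (days) |
|---|---|---|---|
| 1% | 1.08 | 4% | not tabulated |
| 2% | 1.03 | 9% | not tabulated |
| 3% | 0.99 | 13% | 1.12 |
| 5% | 0.90 | 20-21% | 1.11 |
| 10% | 0.71 | 37% | 1.07 |

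With onset rounded up to whole days, the loss at 10% is 40%.

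A second model (Weibull shape 2, 95% daily sensitivity after onset, mean onset restricted to Day 14) gives these shares of the true difference retained at 2%, 5% and 10%:
- Medians 3 and 4 days: 91%, 79%, 62% under the first-day rule; 100%, 99%, 96% under the two-day rule.
- Medians 5 and 7 days: 86%, 68%, 48% under the first-day rule; 99%, 97%, 93% under the two-day rule.

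**Medians.** SAP 8.6.3 names the Kaplan-Meier median. In the lognormal model it is 3 versus 4 days under the first-day rule and 4 versus 5 under the two-day rule at every rate from 1% to 10%, so the difference is one day either way. In the Weibull model with medians 5 and 7, the first-day rule gives 5 versus 7 at 2% but 5 versus 6 at 5% and 4 versus 5 at 10%. Whole-day medians are coarse and can shift by a day through rounding alone.

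**5. Supervision.** Protocol 12.5.1 has entries made daily between visits. Protocol 12.7 describes every procedure as performed under site supervision. Both cannot be true of the diary.

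**The case against.** The case against making much of this is substantial.

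- **The first-day rule is inferred.** A reader might take SAP 8.6.3 to say that the first single-day dip fixes the onset date. It does not. It gives a threshold and says the diary is used in addition to the clinic visits. What stands is that the derivation is unspecified.
- **Bias is not established.** A reader might conclude that the diary comparison is pulled early and blurred between arms. That depends on a stray-rating rate, an onset distribution and a true difference, none of which the documents give. At 1-2% per day the loss is modest. If the products have the same onset there is no difference to shrink. The gain from confirmation assumes independent daily errors; a subject who consistently over-rates improvement passes a two-day rule.
- **Early collection mainly costs information.** A reader might infer that it distorts the curve. Censoring at the last entry does not bias Kaplan-Meier if visit timing is unrelated to onset, and clinic self-ratings at Weeks 2 and 4 still catch later onset, more coarsely.
- **Safeguards exist.** Subjects are blinded and trained in self-rating and diary use (Protocol 9.3.1, 12.5.1, 13.1.1). Diaries are checked for completeness. Separate clinic-based onset analyses are planned, and the efficacy analyses are declared exploratory (SAP 8.6.1).

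These points limit the size of the issue and argue against replacing the first-day analysis. They do not resolve the conflict between the window and the 14 required days, or supply the missing rule.

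**Conclusion.** Three things hold on the documents alone: up to 5 of 14 required diary days can be lost within the visit window; SAP 8.6.3 states neither a derivation nor a censoring rule for diary onset; and Protocol 12.7 misdescribes the diary.

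The consequences are conditional. Averaged over an even spread of visits, early collection would lose about 0.2-0.9% of onsets if the median is 3-4 days and about 3.6% if it is 6. Under a first-day rule a stray dip can only move the onset date earlier, and equal error rates in both arms would shrink a true difference. By how much cannot be known from the plan: 4-9% of the mean difference at 1-2% stray ratings per day and 13-40% at 3-10% in the lognormal illustration with medians 3 and 4 days. The difference in medians is unaffected there, though a two-day difference could lose a day at 5-10%.

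This touches one component of one descriptive secondary endpoint and leaves the co-primary analysis unaffected. It merits action because the endpoint is in the title and the corrections are cheap.

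**What to change.** 1. **Protocol 12.5.1, 4.1 and Table 12-1 (and SAP Table 2 to match).** A subject seen for Week 2 before Day 14 keeps the diary through Day 14 and returns it at Week 4, where the completeness check is made. The clinic window stays as it is. Cost: a later return and some risk of a lost diary.
2. **SAP 8.6.3, main diary analysis.** State that diary onset is the first recorded day with at least 1 point improvement from Baseline in the subject's rating at maximum frown, and that subjects without onset are censored at the last diary entry. Cost: two sentences.
3. **SAP 8.6.3, supportive diary analysis.** Alongside the first-day analysis, date onset at the first of two consecutive recorded days with at least 1 point improvement. Cost: one more table, and a missed day can delay confirmed onset.
4. **Protocol 12.7 and SAP 8.5.2.** Except the diary from the statement that procedures are supervised at the site. Cost: wording only.

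For subjects whose diaries have already been collected, only items 2 to 4 can still be applied; reporting how many diaries ended before Day 14 would then show how much was lost.

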### 7.5.1.1 Study Design Justification

This will be a multi-center, randomized, double-blind, comparator-controlled study. The study will take place in the EU, US and Canada.

To allow all subjects to profit from treatment and to obtain adequate data for BoNT/A-DP treatment, the study will be comprised of a double-blinded treatment comparing BoNT/A-DP with [REDACTED] (ratio 1:1). Primary and secondary endpoints will compare efficacy, safety and subject satisfaction after a single treatment of the investigational BoNT/A-DP to an existing commercially available product [REDACTED]

Two hundred subjects will be enrolled, which should allow for a precise estimate of response rate and for post-hoc sensitivity analyses.

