#### **15.4.2 Secondary Outcome Measures**

##### **Key Secondary Analyses:**

Since the focus of the statistical analysis is on descriptive statistics and no formal statistical hypothesis testing is planned on secondary endpoints, no adjustment for controlling the type 1 error rate is required.

The following are considered key secondary endpoints:

1. Percentage of responders with an FWS score of 0 or 1 and a  $\geq 1$  point reduction in FWS score at maximum frown at Weeks 1, 2, 8, 12 and 16, based on independent investigator assessment and subject assessment.
2. Percentage of responders with an FWS score of 0 or 1 and a  $\geq 2$  point reduction in FWS score at maximum frown at Weeks 1, 2, 4, 8, 12 and 16, based on independent investigator and subject assessments.
3. Percentage of responders with an FWS score of 0 or 1 and a  $\geq 1$  point reduction in FWS score at rest at Weeks 1, 2, 4, 8, 12 and 16, based on independent investigator and subject assessments.
4. Time to onset of effect, as measured at Weeks 1, 2, and 4, based on independent investigator and subject assessments. Onset of effect is defined as  $\geq 1$  point improvement in Glabellar Line Scale - Investigator (GLS-I) and Glabellar Line Scale – Subject (GLS-S) score relative to Baseline at maximum frown in glabellar lines. In addition, onset of effect will be assessed by subjects daily during the first 2 weeks after treatment, by recordings in the subject diary.
5. For subjects who respond, duration of effect will be assessed based on independent investigator and subject assessments. Effect will be deemed to be lost when scores return to Baseline values.
6. The FACE-Q assessment at Weeks 4, 12 and 16.

For categorical endpoints, the same analyses will be conducted as described for the co-primary endpoints. Continuous variables will be summarized using the following descriptive statistics: number of subjects (n), mean, standard deviation, median, minimum and maximum. 95% confidence of the difference in treatment effects will be calculated. Time-to-response and duration of response will be analyzed using Kaplan-Meier methodology.

The FACE-Q Satisfaction with Outcome Scale will be derived in accordance with the developers' instructions and missing data treated accordingly.

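### SAP 8.6.3 specifies only n and % for FACE-Q and, without declaring it, leaves out the 95% CI of the treatment difference that protocol 15.4.2 calls for

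*SAP*

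**What the plan says.** **Protocol.** Section 15.4.2 lists FACE-Q as the sixth key secondary endpoint: "6. The FACE-Q assessment at Weeks 4, 12 and 16". The methods that follow are set by type of variable:

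- Categorical: "For categorical endpoints, the same analyses will be conducted as described for the co-primary endpoints". The co-primary analysis in 15.4.1 includes a 95% CI for the difference between products.
- Continuous: "Continuous variables will be summarized using the following descriptive statistics: number of subjects (n), mean, standard deviation, median, minimum and maximum".
- Directly after the continuous rule: "95% confidence of the difference in treatment effects will be calculated". The word interval is missing there; I read it as a 95% CI.
- Onset and duration are assigned to Kaplan-Meier methods.

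Section 7.5.1.1 gives the intent: "Primary and secondary endpoints will compare efficacy, safety and subject satisfaction after a single treatment of the investigational BoNT/A-DP", set against the marketed comparator.

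**SAP.** Section 8.6.3 applies the co-primary analysis to the three Facial Wrinkle Scale (FWS) responder endpoints and Kaplan-Meier to onset and duration. For FACE-Q it says: "The FACE-Q assessment at Weeks 4, 12 and 16 will be analyzed descriptively (n and % will be presented". The next sentence reads: "The FACE-Q Satisfaction with Outcome Scale will be derived in accordance with the developers' instructions and missing data treated accordingly". SAP 8.1 limits its CI for a treatment difference to proportions at Week 4. SAP Section 9 lists three changes from the protocol: no composite endpoint, added country and region subgroups, and Newcombe in place of Clopper-Pearson. FACE-Q is not among them.

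**The concern.** The SAP has a scale score produced and then specifies counts and percentages, without saying what they count. The protocol's interval for the difference has no counterpart.

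FACE-Q is the trial's only satisfaction measure, and protocol 12.5.2 names it as one of two patient-reported instruments meant to support label claims. The study tests no hypotheses, so its comparative output consists of estimates with intervals. An endpoint with neither a planned difference nor a planned interval yields two columns of figures and leaves the reader to judge the gap. If the difference were added after unblinding, the choice of score, summary and visit could be influenced by the results.

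**Working it through.** **1. The plan's own precision figure.** Inputs from SAP Section 5: 100 per group, 81.5% expected in both, two-sided 95%, normal approximation.

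Half-width = 1.96 × √(2 × 0.815 × 0.185 / 100) = 1.96 × √0.0030155 = 1.96 × 0.0549 = 0.1076, or 10.8%.

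The stated 10.8% reproduces (Newcombe gives 10.8% too). It belongs to the co-primary responder endpoints; no precision figure is given for FACE-Q.

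**2. Which rule in protocol 15.4.2 covers FACE-Q?** Endpoints 1 to 3 are responder percentages, so categorical. Endpoints 4 and 5 are time-to-event. That leaves endpoint 6, FACE-Q. Vital signs have their own rule later in the section. FACE-Q is therefore the only listed efficacy endpoint that the continuous rule can serve, although the protocol does not say so by name.

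**3. Does the classification matter for the interval?**

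| Reading of FACE-Q | Protocol 15.4.2 | SAP |
|---|---|---|
| Continuous score | By-arm descriptive statistics and 95% CI of the difference | 8.6.3: n and %. 8.1 may supply mean and SD. No CI of the difference |
| Categorical | Co-primary analysis, including 95% CI of the difference | 8.6.3: n and %. Co-primary analysis given to the FWS responder endpoints only |

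Under both readings the protocol plans an interval for the difference and the SAP does not. The provision in SAP 8.1 does not fill the gap: it concerns proportions, not a scale score, and Week 4, not Weeks 12 and 16.

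**4. What precision would a restored interval have?** For a difference in means with equal arms of size n and a common SD:

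Half-width = t(0.975, 2n − 2) × √(2/n) × SD

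| Subjects per arm with a score | Half-width |
|---|---|
| 100 | 1.972 × 0.1414 = 0.279 SD |
| 90 | 0.294 SD |
| 80 | 0.312 SD |

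The documents give no FACE-Q SD. Purely as assumptions, with 100 per arm:

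| Assumed SD (points) | Half-width (points) |
|---|---|
| 10 | 2.8 |
| 15 | 4.2 |
| 20 | 5.6 |
| 25 | 7.0 |
| 30 | 8.4 |

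If a response category were analysed as a proportion instead, the Newcombe half-width with 100 per arm and equal observed rates would be 13.6 percentage points at 50%, 12.6 at 70%, 11.1 at 80% and 8.7 at 90%. An interval is feasible at the planned size under either reading.

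**The case against.** The strongest reply is that the SAP is ambiguous here and has deleted nothing. SAP 8.1 still prescribes mean, median, SD and range for continuous variables, and 8.6.3 promises suitable descriptive statistics for the secondary endpoints. The FACE-Q sentence says n and % will be shown, not that nothing else will. The table shells are in a separate document. The protocol never labels FACE-Q continuous, its synopsis gives the other endpoints descriptive statistics without an interval, and the sixth objective lacks the comparator wording of most of the others. All six secondary efficacy endpoints are called key in 15.4.2, and the SAP calls the efficacy analyses exploratory.

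Much of this stands, and it rules out three stronger readings that a reader might infer:

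- *That the mean and SD have been dropped.* The documents do not show this. SAP 8.1 can be read as covering the derived score, and no text says the FACE-Q sentence overrides it.
- *That the arms will not be compared in any form.* SAP 8.1 presents summaries by treatment group, so both arms appear side by side. It also allows within-arm 95% CIs where relevant. No hypothesis test was ever planned.
- *That the derived score goes unused.* SAP 8.1 puts derived data in the subject listings, so the score is at least listed.

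Nor can one be sure what the percentages would count. Protocol 23.3 shows one agree or disagree answer per statement, which suits n and %, but the items and the developers' scoring rules are not in the documents.

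The reply does not recover the interval for the difference. If SAP 8.1 does supply n, mean and SD by arm, a reader could compute that interval, but this is not the same as planning it. The synopsis is weaker than 15.4.2, but 15.4.2 is the detailed methods text, and 7.5.1.1 says satisfaction will be compared.

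**Conclusion.** The point holds in this form: the SAP names no analysis variable for FACE-Q, plans no between-group estimate or CI for it, and does not declare the departure from protocol 15.4.2. Whether a mean and SD will be reported by arm is unclear, not excluded.

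The conclusion about the interval does not depend on whether FACE-Q is continuous or categorical. It does rest on reading the protocol's incomplete phrase as a 95% CI and on taking 15.4.2 over the shorter synopsis. A restored interval would have a half-width of about 0.28 SD with 100 scored subjects per arm, rising to about 0.31 SD with 80, assuming equal arms and a common SD. These figures show that the comparison is feasible; they do not measure a bias.

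The co-primary analysis is unaffected. The point is worth acting on because it concerns the sole satisfaction endpoint and the remedy is small.

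**What to change.** In SAP 8.6.3, replace the FACE-Q sentence with text to this effect: the derived FACE-Q score at Weeks 4, 12 and 16 will be summarised by arm (n, mean, SD, median, minimum, maximum), with the difference in means between BoNT/A-DP and the comparator and its two-sided 95% CI; item responses will also be shown as n and %. Keep the sentence on the developers' scoring and missing-data rules. FACE-Q is not collected before treatment, so the comparison is of post-treatment scores and needs no change-from-baseline derivation.

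If the sponsor does not want a between-group estimate, SAP Section 9 should list the omission as a change from protocol 15.4.2 and give the reason.

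The cost is one sentence and one extra table. No new data, visits or subjects are needed, and with no hypothesis testing planned, no multiplicity adjustment follows.
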